Purpose of drug/substance use in this study	
Work in our group has revealed that short-term (7-day) administration of antidepressants produces positive biases in the processing of emotional information in healthy volunteers. Such effect might be an important neuropsychological mechanism of antidepressant action.
 
The current study will investigate the effect of seven-day administration of atorvastatin 20mg on emotional and reward processing tasks in healthy volunteers. There is evidence that statins may exert antidepressant effects via anti-inflammatory and anti-oxidant pathways, and it is therefore predicted that atorvastatin will have positive effects on emotional and reward processing.
	
Adverse reactions and side effects posing a particular risk with this treatment	
Muscle pain or weakness: usually mild and quickly responding to stopping or switching medication
 
Elevation of liver transaminases: significant only in case of pre-existing hepatic disease
 
Rhabdomyolysis: very rare but severe myopathy associated with elevated creatine kinase and myoglobinuria
 
Nasopharyngitis, epistaxis, pharyngo-laryngeal pain: usually mild and quickly responding to stopping or switching medication
 
Headache: usually mild and quickly responding to stopping or switching medication
 
Gastrointestinal disturbances (constipation, diarrhoea, flatulence, dyspepsia, nausea): usually mild and quickly responding to stopping or switching medication
 
New-onset diabetes mellitus: in predisposed individual with pre-existing hyperglycaemia
 
Haemorrhagic stroke: in patients with prior haemorrhagic stroke or lacunar infarct
	

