The behavioural tasks will include the Oxford Emotional Test Battery (ETB), which has previously been found to be sensitive to the effects of antidepressants, and a reward task of Probabilistic Instrumental Learning (PIL). The ETB involves the presentation of emotion-related words and pictures of faces with different expressions. The reward task involves repeatedly choosing between two options and there is the possibility of winning up to £10 depending on the choices made (see 'Expenses and Benefits' below). All stimuli will be presented on a computer screen and participants will be required to respond via button presses on a keyboard.

Participants will be asked to report their adherence to the 7-day administration of atorvastatin/placebo.

At the end of the research visit, a member of the study team will ask participants to try to guess which treatment they received, as a measure of how successful the blinding was.

Sample Handling

Blood samples (4mL = i.e. 1 teaspoon) taken during the Screening Visit and the Research Visit for investigating hs-CRP will be handled at the Neurosciences Building's laboratory. On the same day, they will be rendered acellular by centrifugation on receipt and stored at -30°C until assay. Any excess material remaining at the end of the study will be disposed of by the laboratory within 6 months according to the Human Tissue Authority guidelines. The samples will be stored in a freezer at the Neurosciences Building in an anonymised form. Access to the samples will be by the research team and the samples will be in the custody of [name] who will hold the key code linking the samples to a particular individual. The samples will be analysed for once all participants have completed the study.

Female participants will be required to give a urine sample for a pregnancy test at the Screening Visit. Urine samples will be destroyed immediately after the test result has been obtained.

Discontinuation/Withdrawal of Participants from Study

Each participant has the right to withdraw from the study at any time. In addition, the Investigator may discontinue a participant from the study at any time if the Investigator considers it necessary for any reason including:

- Pregnancy

- Ineligibility (either arising during the study or retrospectively having been overlooked at screening)
- Significant protocol deviation
- Significant non-compliance with treatment regimen or study requirements
- Withdrawal of Informed Consent

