9. STATISTICS AND ANALYSIS

Do you have a statistical plan?

Yes No

If no, please justify.

The IBM SPSS statistical software will be used to analyse all behavioural data. Demographic and baseline measures will be analysed using independent t-tests.

Mood, anxiety, side-effects, and hs-CRP measures will be analysed using repeated measures analysis of variance (ANOVA).

Behavioural task results will be analysed using between-groups analysis of variance (ANOVA).

Any significant interactions will be followed up using simple main effect analyses. When assumptions of equality of variances are not fulfilled, the Greenhouse-Geisser procedure will be used to correct the degrees of freedom.

Number of Participants

50 healthy volunteers (25 per group)

Have you done a sample size calculation?

Yes No

If yes, please give details below

If no, please give details to indicate you have considered the implications the selected sample size will have on the study outcome

We will be using the Oxford Emotional Test Battery, which is a well-validated set of emotional processing tasks that are sensitive to antidepressant effects. On the facial expression recognition task, one of the main outcome variables is accuracy at recognising fearful facial expressions and a sample size of 25 per group would give 0.9 power to detect changes of the magnitude of those we have seen in a previous antidepressant healthy volunteer study [drug mean 10.64 (SD 9.77) vs placebo mean 3.36 (SD 5.96) (Harmer-2004).

Analysis of Outcome Measures

Data analysis will take place at the University of Oxford, Department of Psychiatry, and will be undertaken by the research team under the supervision of the Principal Investigator. All data will be analysed using a between-groups analysis of variance (ANOVA).

Withdrawn participants' data will not be included in the analysis.

The primary outcome measure is performance (accuracy and reaction time) in computer-based tasks of emotional processing in the comparison between drug and placebo groups. Secondary to this is performance (accuracy and reaction time) in a computer-based task of reward processing in the comparison between drug and placebo groups, and changes in high sensitivity-C Reactive Protein (hs-CRP) from baseline to seven-day in the comparison between drug and placebo groups.

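### The between-groups ANOVA named for the primary task data has no expression or valence term, and it conflicts with the interaction, Greenhouse-Geisser and repeated-measures statements around it

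*Combined protocol and SAP*

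**What the plan says.** All the analysis statements are in section 9 (Statistics and Analysis) of the combined protocol and SAP.

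- Primary outcome: "The primary outcome measure is performance (accuracy and reaction time) in computer-based tasks of emotional processing in the comparison between drug and placebo groups".
- Model for the task data: "Behavioural task results will be analysed using between-groups analysis of variance (ANOVA".
- The sentence just before it treats other outcomes differently: "Mood, anxiety, side-effects, and hs-CRP measures will be analysed using repeated measures analysis of variance (ANOVA".
- The two sentences just after it: "Any significant interactions will be followed up using simple main effect analyses", and "When assumptions of equality of variances are not fulfilled, the Greenhouse-Geisser procedure will be used to correct the degrees of freedom".
- Under the sub-heading on analysis of outcome measures: "All data will be analysed using a between-groups analysis of variance (ANOVA".

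On the data themselves, section 6 (Study Procedures, subsequent visits) says: "The ETB involves the presentation of emotion-related words and pictures of faces with different expressions". On the rationale, the synopsis reports that seven days of antidepressant treatment "produces positive biases in the processing of emotional information in healthy volunteers". Section 4 describes earlier drug effects on negative faces and on recall of negative relative to positive material.

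The plan names no within-person factor for the tasks, no treatment-by-valence contrast and no bias score. The sample size rests on one score, fear-recognition accuracy, which is described as one among the main outcome variables.

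**The concern.** The study has two treatment groups and no other between-groups factor. A between-groups ANOVA on a task score therefore has one effect, treatment, and no interaction to follow up. Greenhouse-Geisser also has nothing to act on, because it corrects for non-sphericity across a within-person factor with three or more levels. The plan ties it to equality of variances, which is a different assumption.

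Because the author separates repeated measures from between-groups ANOVA in adjacent sentences and puts the tasks in the second class, the label is hard to dismiss as shorthand. The later sentence that gives all data a between-groups ANOVA then contradicts the repeated measures assigned to mood, anxiety, side-effects and hs-CRP.

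Two things are at stake for the primary outcome. If each expression is tested separately, the chance of some false-positive result grows with the number of tests. And a result that is significant for one expression but not for another does not show that the drug effect differs between them. That difference is what a claim about emotional bias needs.

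**Working it through.** **1. The plan's own power figure.** Inputs from section 9: 25 per group; drug mean 10.64 (SD 9.77); placebo mean 3.36 (SD 5.96). Alpha is not stated; 0.05 two-sided is assumed.

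- Difference = 10.64 − 3.36 = 7.28
- Pooled SD = √[(9.77² + 5.96²)/2] = √65.49 = 8.09
- Standard error = 8.09 × √(2/25) = 2.29
- Power = Φ(7.28/2.29 − 1.96) = Φ(3.18 − 1.96) = 0.889

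This agrees with the stated 0.9. It is the power for a two-group comparison of one score.

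**2. What each sentence needs.**

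| Statement in section 9 | What it requires | In the model named for the tasks? |
|---|---|---|
| Follow-up of interactions | At least two factors | No, treatment only |
| Greenhouse-Geisser | A within-person factor with three or more levels | No |
| Between-groups ANOVA for all data | No repeated measures anywhere | Conflicts with the repeated measures sentence |

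**3. Separate tests per expression.** The number of expressions is not stated, so k is an assumption. For independent tests at 5%, the chance of at least one false positive is 1 − 0.95^k:

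- k = 4: 1 − 0.815 = 19%
- k = 6: 1 − 0.735 = 26%
- k = 12 (for example, six expressions by accuracy and reaction time): 1 − 0.540 = 46%

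Scores from one person will usually be correlated, which lowers these figures. With an assumed common correlation of 0.5 between the test statistics they are about 16%, 21% and 32%.

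**4. Power for a two-level treatment-by-valence test.** This test is the same as a between-groups test on each person's negative-minus-positive score. Assumptions: the effect of 7.28 falls on negative stimuli only; the SD is 8.09 for each valence; the within-person correlation ρ is unknown. Then SD of the difference = 8.09 × √[2(1 − ρ)], and power = Φ(7.28/[SD × √(2/25)] − 1.96).

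| ρ | SD of difference | Power, 25 per group | n per group for 0.9 |
|---|---|---|---|
| 0 | 11.44 | 0.61 | 52 |
| 0.2 | 10.24 | 0.71 | 42 |
| 0.3 | 9.58 | 0.77 | 37 |
| 0.5 | 8.09 | 0.89 | 26 |
| 0.7 | 6.27 | 0.98 | 16 |

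The interaction matches the power for fear accuracy only when ρ = 0.5. An effect spread over both valences, or acting in opposite directions, would change these figures.

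**The case against.** The best defence is that a mixed ANOVA was intended and loosely labelled by its between-groups factor. Mood, anxiety, side-effects and hs-CRP are taken at two visits only (section 6), and a two-level time factor raises no sphericity question. The Greenhouse-Geisser sentence makes most sense if expressions are the repeated factor. This is plausible, but the plan never says so, and on that reading the intended model contradicts the one named. If the sentences instead cover only the two-visit measures, the tasks have no stated valence test. The text needs correcting either way.

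A reader might go further in three ways that the documents do not support.

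- *That the named model cannot test a valence effect.* It can, if applied to a per-person negative-minus-positive score. A between-groups test of fear accuracy alone is also valid. The gap is that no such score is defined.
- *That a treatment-by-valence interaction is the stated hypothesis.* Section 4 predicts only a positive effect on emotional and reward processing. Valence specificity is a fair inference from the rationale, which describes other drugs.
- *That expressions would be analysed as if they came from different people, making the tests too liberal.* Nothing in the plan suggests this. It would also make the interaction test conservative: in a simulation with two valences and 25 per group, its type I error at a nominal 5% fell to about 1.9% at ρ = 0.3 and 0.7% at ρ = 0.5.

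Section 4 calls the study exploratory, which softens the multiplicity point. It does not remove the need to say which model will be fitted to the primary outcome.

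**Conclusion.** The concern holds as a mis-specified and internally inconsistent primary analysis. Because the model named conflicts with the sentences around it, this is more than missing detail. The 19%, 26% and 46% figures depend on the literal reading, on assumed counts of tests and on independence, so they are upper-end illustrations and not predictions for this trial.

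The interaction figures do not show that the trial is underpowered. They depend on an unstated correlation and on an effect confined to one valence, and the sample size reproduces for the score it was built on. They show only that the 0.9 cannot be carried over to a valence contrast without further information.

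The correction should be made before unblinding, since the choice between single expressions, a bias score and an interaction is otherwise left to the analyst.

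**What to change.** For each emotional task, state a mixed ANOVA or mixed model with treatment between participants and expression or valence within participants, and name treatment-by-valence as the test of bias. Alternatively, pre-define a per-person negative-minus-positive score and keep the between-groups ANOVA for that score. In addition:

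- Keep fear accuracy as a pre-specified comparison that does not depend on a significant interaction. It is the only comparison the plan powers, and gating could block it.
- Apply Greenhouse-Geisser when sphericity fails, for within-person factors with three or more levels.
- Delete the sentence that assigns all data to a between-groups ANOVA, or reconcile it with the repeated measures sentence.
- State that the 0.9 power applies to the single fear-accuracy score, and give power for the chosen contrast over a range of correlations.

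The cost is wording plus a short power statement, with the same data and software. The downside is that power for the valence contrast may prove lower than 0.9 if the within-person correlation is below about 0.5. A mixed model per task also leaves multiplicity across tasks, and across accuracy and reaction time, to be dealt with separately.

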2. SYNOPSIS

Please state why this study is not considered a Clinical Trial of an Investigative Medicinal Product
	
This study is not a Clinical Trial of an Investigative Medicinal Product as we are not investigating the efficacy of atorvastatin but using it as a pharmacological tool to understand the role of inflammation in emotional and reward processing.
 
This study does not fit the MHRA definition of a clinical trial as one designed to: discover or verify/compare a drug's clinical effects; to discover or verify/compare its pharmacological effects (e.g. pharmacodynamics); to identify or verify/compare its adverse reactions; or to study its absorption, distribution, metabolism or excretion (https://www.gov.uk/government/uploads/system/uploads/attachment_data/file/317952/Algothrim.pdf).
	

List all sites where study will be conducted
	
Neurosciences Building, Department of Psychiatry, University of Oxford, Warneford Hospital, [name]
	

Age Range of Study Participants
	
18-50 years old
	

Planned Sample Size
	
50 healthy volunteers (25 per group)
	

Planned Study Duration (n.b. A minimum approval period of 1 year and maximum of 5 years can be granted)
	
24 months
	

Anticipated Start Date
	
1st February 2019
	

Anticipated End Date
	
1st February 2021
	
	
Objectives
	
Outcome Measures

Primary
	
To investigate the effects of seven-day atorvastatin administration on emotional processing
	
Accuracy and reaction times on computer-based tasks of emotional processing (e.g. facial expression recognition, emotional categorisation and memory), comparing those receiving drug and placebo.

Secondary
	
To investigate the effects of seven-day atorvastatin administration on reward processing
	
Accuracy and reaction times on computer-based tasks of reward processing comparing those receiving drug and placebo.

	To investigate the effects of seven-day atorvastatin administration on inflammation	Changes in high sensitivity-C Reactive Protein (hs-CRP) from baseline to seven-day, comparing those receiving drug and placebo
Name of drug/substance	Atorvastatin	

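### The primary outcome spans accuracy and reaction time across a whole emotional battery, with no lead score, alpha, multiplicity control or success rule, and the stated power covers only fearful-face accuracy

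*Combined protocol and SAP*

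**What the plan says.** All references are to the combined protocol and SAP.

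- **Primary outcome.** Section 9 (Analysis of Outcome Measures): "The primary outcome measure is performance (accuracy and reaction time) in computer-based tasks of emotional processing", compared between drug and placebo. The Synopsis has "Accuracy and reaction times on computer-based tasks of emotional processing (e.g. facial expression recognition, emotional categorisation and memory"; the three tasks are examples, so the list is open.
- **Instrument.** Section 6 (Subsequent Visits): "The behavioural tasks will include the Oxford Emotional Test Battery (ETB" and "The ETB involves the presentation of emotion-related words and pictures of faces with different expressions". Section 9 confirms the battery: "We will be using the Oxford Emotional Test Battery, which is a well-validated set of emotional processing tasks". The individual scores it yields are not listed or ranked.
- **Model.** Section 9: "Behavioural task results will be analysed using between-groups analysis of variance (ANOVA". Significant interactions are followed by simple main effects, with a Greenhouse-Geisser correction where needed. No significance threshold is given, and no effect is named as the one that answers the primary objective.
- **Power.** Section 9 (Number of Participants) introduces the planning variable in these words: "one of the main outcome variables is accuracy at recognising fearful facial expressions". For that variable alone it then makes its power claim: "a sample size of 25 per group would give 0.9 power to detect changes of the magnitude". The reference is an earlier antidepressant study in healthy volunteers. The planning values are mean 10.64 (SD 9.77) on drug and 3.36 (SD 5.96) on placebo.
- **Framing.** Section 4 calls the study exploratory but predicts a positive effect on emotional and reward processing. The Synopsis says that efficacy is not under investigation.

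**The concern.** The battery is fixed, but the result that decides the primary objective is not. A difference in fear recognition, in another expression, in categorisation speed or in memory could each be presented as the primary finding. A reader could not tell a choice planned in advance from one made after seeing the data.

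The analysis text does not settle this. An ANOVA is a model, not a decision rule. The plan leaves open whether a group main effect, a group-by-emotion interaction or a simple effect within one emotion counts. Greenhouse-Geisser adjusts degrees of freedom and does nothing about multiplicity.

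The power figure adds to the difficulty. It is the only one given and could be read as the power for the primary outcome. It belongs to a single score, which the protocol itself describes as one among several main variables.

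**Working it through.** **Inputs.** From section 9: means 10.64 and 3.36, SDs 9.77 and 5.96, 25 per group, stated power 0.9. Assumed, because the documents do not state it: two-sided 5%.

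**1. Reproduce the stated power.**

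- Difference: 10.64 − 3.36 = 7.28
- Pooled SD: √[(9.77² + 5.96²)/2] = √[(95.45 + 35.52)/2] = √65.49 = 8.092
- Standardised difference: d = 7.28/8.092 = 0.900
- Noncentrality: d × √(25/2) = 0.8996 × 3.536 = 3.181
- Normal approximation: Φ(3.181 − 1.960) = Φ(1.221) = 0.889
- Noncentral t, 48 df: 0.876
- Welch t, 39.7 df: 0.873

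The stated 0.9 is therefore about right for this score, tested once and without adjustment.

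**2. What 25 per group offers other scores.** The documents give no planning effect for any other score, so the effects below are assumed (noncentral t, two-sided 5%).

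| d | Power |
|---|---|
| 0.8 | 0.791 |
| 0.7 | 0.679 |
| 0.5 | 0.410 |

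The smallest d with 80% power is 0.809. The 0.9 does not carry over to a score with a smaller effect.

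**3. What an unranked set of scores could do to the error rate (illustration only).** Assume that any score significant at 5% counts as a positive primary result, and that the test statistics are normal with equal pairwise correlation ρ. The chance of at least one false positive among k tests is 1 − P(all |Z| < 1.96). At ρ = 0 this is 1 − 0.95^k; otherwise it is found by one-factor integration.

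| k | ρ = 0 | ρ = 0.3 | ρ = 0.5 | ρ = 0.8 |
|---|---|---|---|---|
| 3 | 0.143 | 0.136 | 0.125 | 0.098 |
| 6 | 0.265 | 0.241 | 0.207 | 0.139 |

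Six corresponds to the Synopsis's three example tasks times two measures. The true number of scores is not stated; splitting by emotion or valence would raise it.

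**The case against.** The strongest reply is that this is a mechanistic, exploratory study with no treatment or licensing decision attached, so a formal success rule and familywise control are partly a matter of taste. That lowers the weight of the point. It does not remove it, because the protocol still designates a primary outcome, predicts a direction and quotes a power, and none of these can be interpreted without a named score and a significance level.

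Second, the ANOVA with follow-up only after a significant interaction may give some gatekeeping within a task. That is a fair reading, but it gives no control across tasks or between accuracy and reaction time. It also means that the error rates above rest on an assumed rule, so they should not drive severity.

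Third, the power statement is correct for its own score and does not explicitly claim more. That stands: the fault is in what it leaves uncovered.

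Fourth, reducing a domain objective to one fearful-face score is only one possible remedy. A short listed family with adjustment, or a named group-by-emotion interaction, would also close the gap. A shared family has a price, however. With Bonferroni over six scores (0.05/6 = 0.0083), power for fearful-face accuracy at 25 per group falls to 0.67 (t) or 0.71 (normal), and 90% power needs about 38 to 40 per group. The single-score route avoids this.

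**Conclusion.** The concern holds and should be fixed. The documents contain no lead score, alpha, multiplicity control, deciding effect or success rule for the primary outcome. Their only power, 0.88 to 0.89 on recalculation, applies to fearful-face accuracy alone.

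The recalculation assumes a two-sided 5% level and takes the planning means and SDs at face value. The error-rate illustration, about 10% to 14% for three tests and 14% to 26% for six, also depends on the assumed rule, counts and correlations; it shows the possible scale and is not an estimate for this trial. The absence of a named primary score does not depend on any of these assumptions.

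**What to change.** Before unblinding:

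1. Confirm that the planning figures are for fearful-face recognition accuracy. If they belong to another score, redo the power before naming the primary. The direction also needs checking, as a separate query: the drug mean in section 9 is the higher one, while section 4 cites reduced recognition of negative expressions on antidepressants.
2. Once that is confirmed, name fearful-face accuracy as the single primary outcome, tested at two-sided 5%, because the sample size rests on it. State that the power applies to that one test only.
3. List all other emotional-task accuracy and reaction-time scores as secondary with Holm or false-discovery-rate control, or label them exploratory and report every one.

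If the data are already unblinded, disclose any choice of primary score as post hoc. The documents do not say where the study stands; the anticipated end date is 1st February 2021.

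**Cost.** A protocol amendment, submitted and where necessary approved as section 12 (Approvals) requires. No extra participants or data are needed. The downside is that an effect seen only in memory, categorisation or reaction time could no longer be claimed as the primary result.
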